### **3.3. The Pharmacokinetic Analysis Set (PKAS)**

The PK analysis set includes all randomized patients who received any study drug and who had at least one non-missing drug concentration result following the first dose of study drug.

### **3.4. The Immunogenicity Analysis Set**

The ADA analysis set (AAS) will consist of all patients who received any study drug and who had at least one non-missing ADA result after the first dose of the study drug. Patients will be analyzed according to the treatment they actually received.

The neutralizing antibody (NAb) analysis set (NAS) includes all patients who received any study drug and who tested negative at all ADA sampling times or tested positive for ADA with at least one non-missing result in the NAb assay after the first dose of the study drug; note that, patients who are ADA negative are set to negative in the NAb analysis set. Patients will be analyzed according to the treatment they actually received.

### **3.5. Subgroups**

Subgroups are defined by key baseline factors recorded on the eCRF (unless otherwise specified) and listed as follows. The analysis for the subgroups defined may not be performed if the number of patients within the subgroup is small, e.g. <10 patients per treatment arm. No subgroup analysis will be performed if the study fails to meet its primary objective.

Subgroups to be considered for both efficacy and safety analyses:

- Age group (>6months- <2years, 2years-<6years)
- Sex (Male, Female)
- Ethnicity: Hispanic or Latino (no/yes)
- Race (White, Black, Asian, Other)
- Duration of AD (< 3 years, ≥3 years)
- Baseline BMI (overweight: ≥ 85 percentile of BMI for ≥2 years based on age and gender, ≥ 95 percentile of weight based on length (height), age and gender for < 2 years, Not overweight: not meeting the criteria of overweight ) [based on CDC (Center for Disease control and Prevention) chart]

- Baseline weight group ( $\geq 5$ - $<15$ kg,  $\geq 15$ - $<30$ kg)

Subgroups listed for primary and key secondary efficacy endpoints:

- Age of disease onset ( $<2$  years,  $\geq 2$ years)
- Family history of atopic disease (Yes/No)
- Region (North America, Europe)
- Baseline EASI ( $<25$ ,  $\geq 25$ )
- Baseline worst scratch/itch scale ( $<7$ ,  $\geq 7$ )
- Body Surface Area (BSA) ( $\geq 10\%$ - $<30\%$ ,  $\geq 30\%$ - $<50\%$ ,  $\geq 50\%$ )
- Baseline SCORAD score ( $<50$ ,  $\geq 50$ )
- Previous usage of ciclosporin (CsA) (Yes, No)
- Previous use of systemic immunosuppressants (Systemic Corticosteroid and Systemic Non-Steroidal Immunosuppressant) for AD (Yes, No)
- History of asthma (Yes, No)
- History of allergic rhinitis (Yes, No)
- History of food allergies (Yes, No)

In addition, for analysis of conjunctivitis TEAEs, sub-group analysis based on medical history of conjunctivitis (yes/no) may be performed. TEAE and overall AE summary will be provided by history of food allergies subgroup.

## 4. ANALYSIS VARIABLES

### 4.1. Demographic and Baseline Characteristics

The following demographic and baseline characteristics variables will be summarized:

- Demographic variables: Age at screening (year), Age group (>6m-<2Y, 2Y-<6Y), Sex (Male, Female), Ethnicity (Hispanic or Latino, Not-Hispanic or Latino), Race (White, Black or African American, Asian, Other), Region (North America, EU), Baseline weight (kg), Baseline weight with grouping (>5-15 kg, >15-30 kg), height (m), BMI [for  $\geq 2$  years, BMI will use weight/ height formula; for <2 yrs., BMI will use weight for length formula (weight/length)], BMI with grouping (overweight, not overweight) [using the separate formula by age as described previously]
- Baseline characteristics: Duration of AD disease with grouping (< 3 years,  $\geq 3$  years), worst scratch/itch NRS score, Investigator's Global Assessment (IGA) score [IGA = 3, 4], Eczema Area and Severity Index (EASI) score, SCORing Atopic Dermatitis (SCORAD) score, Body Surface Area (BSA) affected by Atopic Dermatitis, Caregiver global impression of disease (CGID), Patient Oriented Eczema Measure (POEM), Children's Dermatology Life Quality Index (CDLQI for patients  $\geq 4$  years of age), Infants' Dermatology Quality of Life Index (IDQOL for patients <4 years of age), Global Individual Signs score (GISS), Dermatitis Family Index (DFI), NRS Skin Pain, NRS Sleep, Patients with inadequate response to topicals (Yes/No), Pediatric Asthma Symptom Questionnaire (PASQ, only for patients with ongoing asthma), Caregiver-Reported Nasal Symptom Questionnaire (CNSQ, only for patients with allergic rhinitis)

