4.2.1. Inclusion Criteria

A patient must meet the following criteria to be eligible for inclusion in the study:

1. Male or female ≥ 6 months to <6 years of age at the screening visit
2. Diagnosis of AD according to the American Academy of Dermatology consensus criteria at the screening visit
3. Patients with documented recent history (within 6 months before the screening visit) of inadequate response to topical AD medication(s)

NOTE:

- Patients who are unable to achieve and/or maintain remission and low disease activity (comparable to IGA 0=clear to 2=mild) despite treatment with a daily regimen of medium to higher potency TCS (\pm TCI as appropriate), applied for at least 28 days of use, or for the maximum duration recommended by the product prescribing information, whichever is shorter, will meet the definition of inadequate response for the purpose of this study.
- Patients with documented systemic treatment for AD in the past 6 months are also considered as inadequate responders to topical treatments and are potentially eligible for treatment with dupilumab after appropriate washout.
- Acceptable documentation includes contemporaneous chart notes that record topical medication prescription and treatment outcome, or investigator documentation based on communication with the patient's treating physician. If documentation is inadequate, potential patients may be offered a course of treatment with a daily regimen of TCS of medium potency (\pm TCI as appropriate*), applied for at least 28 days during the screening period or for the maximum duration recommended by the product prescribing information, whichever is shorter. Patients who demonstrate inadequate response, as defined above, or develop important side effects (eg, significant skin atrophy, systemic effects) during this period will still be eligible for inclusion in the study.

* TCIs are not permitted during the 2-week TCS standardization period. Investigators may substitute TCIs with low potency steroids on areas of skin on which TCIs are typically applied (eg, face, neck, intertriginous, and genital areas).

NOTE: The target population with respect to disease severity differs for part A (severe AD) and part B (moderate-to-severe AD). Therefore, disease severity criteria are specified separately for part A and part B in inclusion criterion 4 to 6 below:

4. IGA score at screening and baseline visits:
 - a. part A: IGA = 4
 - b. part B: IGA ≥ 3
5. EASI score at screening and baseline visits

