### **5. STATISTICAL METHODS**

For continuous variables, descriptive statistics will include the following: the number of patients reflected in the calculation (n), mean, median, standard deviation, first quartile (Q1), third quartile (Q3), minimum, and maximum.

For categorical or ordinal data, frequencies and percentages will be displayed for each category.

All data will be summarized by 2 treatment groups (i.e., dupilumab 200/300 mg Q4W and placebo).

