#### **5.1. Demographics and Baseline Characteristics**

Demographics and baseline characteristics will be summarized by treatment group for the FAS.

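### Baseline BMI is weight/height² from 2 years but weight/length under 2 years; read as written, its mean and SD by arm combine kg/m² with kg/m

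*SAP*

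**What the plan says.** SAP 4.1 lists the demographic variables, with weight in kg and height in m. BMI is one entry with two derivations. From 2 years, "BMI will use weight/ height 2 formula" (the 2 is a superscript). Under 2 years, "BMI will use weight for length formula (weight/length". A separate entry follows for the categorical version: "BMI with grouping (overweight, not overweight) [using the separate formula by age as described previously".

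SAP 5 sets the summary for any continuous variable: "For continuous variables, descriptive statistics will include the following: the number of patients reflected in the calculation (n), mean, median, standard deviation", followed by quartiles and range. SAP 5.1 sets the layout: "Demographics and baseline characteristics will be summarized by treatment group for the FAS". Neither section splits continuous BMI by age.

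Both derivations will be used, because Protocol 4.2.1 admits "Male or female ≥ 6 months to <6 years of age at the screening visit".

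SAP 3.5 defines overweight within each age band: a BMI percentile from 2 years and, under 2 years, a "percentile of weight based on length (height), age and gender for < 2 years". It names the CDC chart as the source.

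**The concern.** Weight/height² and weight/length are different quantities. A mean taken over children measured on both has no unit, and its SD includes the gap between the two scales as well as the spread among children. Both statistics also depend on what fraction of the arm is under 2 years. Two arms with the same body composition but a different share of the youngest children would show different BMI means.

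What is at stake is one line of the baseline table, which readers use to judge whether the arms are comparable and to describe the population. No test, estimate or error rate is involved.

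**Working it through.** The plan states no BMI mean or SD, so there is no figure to reproduce. The check is one of units, followed by an illustration.

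**Units.** Weight in kg and height in m (SAP 4.1) give kg/m² from 2 years and kg/m under 2 years. Since weight/length = (weight/length²) × length, the value for a child shorter than 1 m is numerically below the weight/length² value by the fraction 1 − length. This follows from the definitions alone.

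**Inputs for the illustration.**
- Mean weights from Part A (Protocol 1.2.2): 9.8 kg under 2 years, 17.1 kg from 2 to <6 years. These are not Part B data.
- Lengths, within-group SD and share under 2 years: assumed, because the documents do not give them.

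**One child of 9.8 kg.**

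| Assumed length (m) | weight/length (kg/m) | weight/length² (kg/m²) |
|---|---|---|
| 0.70 | 9.8/0.70 = 14.0 | 9.8/0.49 = 20.0 |
| 0.75 | 13.1 | 17.4 |
| 0.80 | 9.8/0.80 = 12.3 | 9.8/0.64 = 15.3 |
| 0.85 | 11.5 | 13.6 |

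**Combined summary.** Assume 0.78 m under 2 years, 1.04 m from 2 years, and an SD of s = 1.5 within each group.
- Under 2 years, SAP rule: a = 9.8/0.78 = 12.56.
- Under 2 years, weight/length²: 9.8/0.78² = 16.11.
- From 2 years: b = 17.1/1.04² = 15.81.

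With share f under 2 years, the mean is f·a + (1 − f)·b and the SD is √(s² + f(1 − f)(a − b)²). For example, at f = 0.25 the mean is 0.25 × 12.56 + 0.75 × 15.81 = 15.00, and the SD is √(2.25 + 0.1875 × 3.25²) = 2.06.

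| Share under 2 years | SAP rule, mean (SD) | weight/height² for all, mean (SD) |
|---|---|---|
| 5% | 15.65 (1.66) | 15.82 (1.50) |
| 10% | 15.49 (1.79) | 15.84 (1.50) |
| 25% | 15.00 (2.06) | 15.88 (1.51) |
| 50% | 14.19 (2.21) | 15.96 (1.51) |

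With s = 1.0 or 2.0 instead, the SD at 25% is 1.72 or 2.44 under the SAP rule, against 1.01 or 2.00 with one formula.

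**Sensitivity to age mix.** On these assumptions, a difference of 10 percentage points between arms in the share under 2 years moves the SAP-rule mean by 0.10 × (15.81 − 12.56) = 0.32. With weight/height² for all, it moves by 0.10 × (16.11 − 15.81) = 0.03.

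**The case against.** **Pooling is inferred.** The SAP nowhere says that the two values enter one mean, and SAP 5.1 is a general sentence that does not forbid separate rows by age. This stands as a limit on certainty. Still, there is one entry, summarised by arm, with no age split, and a programmer following the text would combine the values.

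**The under-2 wording could be shorthand for the chart percentile in SAP 3.5.** This is possible, but it fits poorly. SAP 4.1 calls it a formula and writes out the ratio, and it lists the grouped variable as a separate entry.

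**Imbalance is limited and visible.** Randomisation is stratified at 15 kg, which partly balances age, and age, age group, weight and height appear in the same baseline summary. This stands, and it reduces the chance of a misleading difference between arms. It does not give the combined mean a unit.

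**The illustration is mostly assumption.** This also stands. Only the weights come from the documents. The percentage gap between the two formulas is simply 1 minus the length in metres, so it should not be read as a bias in body composition.

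A reader might go further and infer that the youngest children would look markedly lean although their BMI is similar to or above that of older children. The documents do not support this. A single combined row shows no under-2 mean, and the direction depends on the assumed length: 20.0 kg/m² at 0.70 m but 15.3 at 0.80 m, against 15.8 for the older group at 1.04 m.

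**Conclusion.** Read as written, the continuous BMI summary is wrong: it averages kg/m² with kg/m. The unit mismatch needs no assumption beyond the natural reading that one listed variable gets one summary per arm. The numerical size does need assumptions. With the lengths used above and 5% to 50% of children under 2 years, the combined mean runs from 15.65 down to 14.19, where a single formula would give 15.82 to 15.96.

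The consequence is small and descriptive. BMI is not a stratification factor, nor a covariate in the CMH test, the ANCOVA or the imputation model (SAP 5.6.1 and 5.6.2). A reader might infer that the overweight subgroup is also corrupted. It is not: each child is classified within his or her own age band against percentiles, and "Not overweight: not meeting the criteria of overweight" is the complement of that rule. The point merits a correction but should not hold up anything else.

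**What to change.** In SAP 4.1, replace the single continuous BMI entry with two: BMI (kg/m²) for children aged 2 years or older, and weight-for-length percentile or z-score for children under 2, from the chart already named in SAP 3.5. State that the two are reported in separate rows, each with its own n, and are not combined. Leave the overweight grouping as it is. The SAP already handles an age-dependent measure this way in the same list, with CDLQI from 4 years and IDQOL under 4 years as separate variables.

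The cost is one extra row in the baseline table and a sentence in the SAP. No new data are needed, and no model, test or alpha allocation changes. SAP 1 allows revision before the database lock for the primary analysis.

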### 4.2. Medical History and Atopic Disease Medical History

Medical history will be coded according to the Medical Dictionary for Regulatory Activities (MedDRA). Information on conditions related to AD including diagnosis of AD and AD treatment history, personal and/or family history of asthma, allergic conjunctivitis, allergic rhinitis, chronic rhinosinusitis, nasal polyps, eosinophilic esophagitis, food allergy, hives and other allergies due to medications, animals, plants, mold, dust mites, etc. are collected. Recent AD topical treatments history within 6 months before the screening visit is also collected. History of treatment with systemic immunosuppressants for AD (cyclosporine, systemic corticosteroids, methotrexate, azathioprine and other treatments) during the last 6 months will also be collected.

### 4.3. Prior / Concomitant Medications and Procedures

Medications/Procedures will be recorded from the day of informed consent until the end of study (EOS) visit. Medications will be coded using WHO Drug Dictionary (WHODD). If a patient takes more than one medication within the same medication class, this patient will be counted only once in the summary. Procedures will be coded using MedDRA.

Prior medications/procedures: medications taken, or procedures performed prior to administration of the first dose of study drug.

Concomitant medications/procedures (CMs/CPs): medications taken, or procedures performed following the first dose of study drug through the EOS visit.

- Concomitant medications/procedures during the 16-week treatment period are medications/procedures taken after the first dose up to the week 16 visit date or date of study day 113 if the week 16 visit date is missing. Medications/procedures taken during the 16-week treatment period and continued afterwards into the follow-up period will be counted only once as concomitant medications/procedures during the 16 week treatment period.
- Concomitant medications/procedures during the follow-up period are medications/procedures taken after the week 16 visit date to end of study.

Prohibited concomitant medications/procedures: Treatment with the following **concomitant medications** is prohibited during the study:

- Treatment with a live (attenuated) vaccine (e.g. Chickenpox (Varicella), Mumps)
- Treatment with an investigational drug (other than dupilumab)
- Treatment with immunomodulating biologics
- Treatment with systemic nonsteroidal immunosuppressant (e.g. cyclosporine, methotrexate) [may be used as rescue]
- Treatment with crisabarole (may be used as rescue)
- Treatment with medium potency, high-potency or very high potency TCS, (medium or high potency TCS may be used as rescue)
- Treatment with TCI (may be used as rescue) [Note: The use of TCI is prohibited during the 2-week screening period leading up to the baseline visit, and the treatment and follow-up periods]
- Initiation of treatment of AD with prescription moisturizers

The following **concomitant procedures** are prohibited during study participation:

- Major elective surgical procedures
- Phototherapy (ultraviolet A and/or ultraviolet B)

For details of permitted and prohibited medications, see [Appendix 1](#).

Rescue treatments (i.e. both medications and procedures):

If medically necessary (i.e. to control intolerable AD symptoms), rescue treatment for AD may be provided to study patients at the discretion of the investigator. The use of rescue treatment is only allowed after day 14 of the study. Investigators will be required to perform an IGA assessment prior to starting rescue treatment and initiate rescue treatment only in patients who either have an IGA score  $\geq 3$  or have intolerable symptoms. If possible, investigators are encouraged to consider

rescue initially with topical treatment (e.g., high potency TCS) and to escalate to systemic medications only for patients who do not respond adequately after at least 7 days of topical treatment. Patients may continue study treatment if rescue consists of topical medications. Patients who receive systemic corticosteroids or systemic non-steroidal immunosuppressive drugs (e.g., cyclosporine, methotrexate, mycophenolate-mofetil, azathioprine, etc.) as rescue medication during the study will be discontinued permanently from the study drug. All patients will be asked to complete the scheduled study visits and assessments whether or not they complete study treatment and whether or not they receive rescue treatment for AD. Investigators should make every attempt to conduct efficacy and safety assessments (e.g., disease severity scores, safety laboratory tests) immediately before administering any rescue treatment. An unscheduled visit may be used for this purpose, if necessary. For the purpose of efficacy analysis, patients who receive rescue treatment during the study will be considered treatment failures.

For the purpose of the efficacy responder analysis, a pre-specified algorithm will be used to classify rescue (details in Section 5.6.1). In addition, a blinded review of all post-baseline medications to adjudicate rescue treatment, based on medical judgement, will be performed to adjudicate rescue. Patients who receive rescue treatment as per this adjudication during the study will be considered as treatment failures.

## 4.4. Efficacy Variables

### 4.4.1. Primary Efficacy Variable

The primary endpoint in the study is:

- Proportion of patients with IGA 0 or 1 (on a 5-point scale) at week 16

For the **EU and EU Reference Market Countries only**, the co-primary endpoints are:

- Proportion of patients with EASI-75 ( $\geq 75\%$  improvement from baseline) at week 16
- Proportion of patients with IGA 0 or 1 (on a 5-point scale) at week 16

### Investigator's Global Assessment (IGA)

The IGA is a static 5-point assessment instrument to rate AD disease severity globally in clinical studies. The ratings (0 = clear, 1 = almost clear, 2 = mild, 3 = moderate, 4 = severe) are an overall assessment of AD skin lesions based on erythema and papulation/infiltration. IGA score will be assessed at the scheduled and unscheduled clinic visits according to [Appendix 3](#).

### Eczema Area and Severity Index (EASI)

The EASI is a validated measure used in clinical practice and clinical trials to assess the severity and extent of AD ([Hanifin 2001](#)). The EASI score calculation is based upon the Physician's Assessment of Individual Signs [erythema (E), induration/papulation (I), excoriation (X), and lichenification (L)], where each sign is scored as 0 = Absent, 1 = Mild, 2 = Moderate, or 3 = Severe, and also upon the Area Score [based on the % (BSA) affected] where 0 = 0% BSA, 1 = 1-9% BSA, 2 = 10-29% BSA, 3 = 30-49% BSA, 4 = 50-69% BSA, 5 = 70-89% BSA, 6 = 90-100% BSA.

For each of major section of the body (head, upper extremities, trunk and lower extremities), EASI score = (E+I+X+L) x Area Score. The total EASI score is the weighted total of the section EASI

using the weights as follows: the head and neck (H), upper extremities (U), trunk (T), and lower extremities (L) are assigned proportionate body surface areas of 20% (H), 20% (U), 30% (T), and 30% (L), roughly consistent with the ‘rule of nines’. The minimum possible EASI score is 0 and the maximum possible EASI score is 72 where a higher score indicates increased extent and severity of atopic dermatitis. The EASI score of each sign (E, I, X and L) can be calculated in a similar way, for example, the EASI score of erythema = weighted sum of E x Area Score at each section.

The EASI will be collected at the scheduled and unscheduled clinic visits according to [Appendix 3](#).

#### 4.4.2. Secondary Efficacy Variables

##### The key secondary endpoints:

- Proportion of patients with EASI-75 ( $\geq 75\%$  improvement from baseline) at week 16 (**not applicable for EU or EU Reference Market Countries**)
- Percent change in EASI score from baseline to week 16
- Percent change from baseline to week 16 in weekly average of daily worst scratch/itch NRS score

##### **Pruritus (worst scratch/itch) NRS score**

Itch will be measured using a worst scratch/itch NRS that was developed and tested for the study-relevant age group. This is an 11-point scale (0 to 10) in which 0 indicates no scratching/itching while 10 indicates worst scratching/itching possible. The parents/caregivers will be asked to:

“Answer the question below based on what you observe and what your child tells you (if applicable):”

“How would you rate your child’s scratching/itching at its worst in the past 24 hours?”

Pruritus will be assessed by the parent/caregiver on a daily basis using an e-diary throughout the entire study (i.e., screening, treatment, and follow-up periods).

Parents/caregivers will be instructed on using the scale to record their child’s pruritus score at the screening visit. Using the e-diary, parents/caregivers will complete the rating scale DAILY through the entire study (screening, treatment, and follow-up periods). Clinical sites will check parent/caregiver data, collected using the e-diary, for protocol compliance and remind parents/caregivers to complete the e-diary throughout the study.

The baseline worst scratch/itch scale score is defined as the prorated average of the worst scratch/itch scale scores reported continuously for 7 days right before the baseline visit (i.e. study day -7 to day -1). For post-baseline worst itch scale score, the weekly mean of daily worst scratch/itch score is calculated as the average of the available reported daily worst scratch/itch score within the week. For example, if there are 3 scores in a week, the prorated average = (score1 + score2 + score3)/3.

